6.4 Caregiver Interview

An optional qualitative interview with caregivers of study subjects will be conducted remotely by telephone. Only caregivers of subjects for whom separate informed consent for

the caregiver interview is completed will be interviewed. Interviews will be conducted by trained moderators from a 3rd party and are anticipated to be approximately up to 60 minutes in duration. The interviews are planned to elicit a better understanding of the observable signs as well as the impact of study drug and RTT both on the study subject and on the caregiver. The interviews will document changes observed by the caregivers over the course of participation in the study and in antecedent trofinetide studies. The interviews will also provide an opportunity to describe the meaningfulness of any improvements that may have occurred from the perspective of the caregiver. Interviews will be audio-recorded and transcribed for analysis. Any personally identifiable health information mentioned during the interview will be redacted by the interviewer prior to transcription of the interview. Furthermore, if any potential adverse events are revealed during the interview, the interviewer will inform the investigator of the potential adverse event. Audio recordings of the interviews will be destroyed following transcription.

Following the analysis of the qualitative data, a summary report that describes the objectives, methods, participants, and results of the qualitative interviews will be prepared and reported separately from the clinical study report.

The caregiver interview will be administered at or before the final study visit (Week 130 [EOT/ET]).

7 ADVERSE EVENTS

7.1 Specification of Safety Parameters

7.1.1 Definition of Adverse Event

An AE is defined as “any untoward medical occurrence in a patient or clinical study participant, temporally associated with the use of study drug, whether or not considered related to study drug”.

An AE can therefore be any unfavorable and unintended sign (e.g., an abnormal laboratory finding), symptom, or disease temporally associated with the use of a drug, without any judgment about causality or seriousness. An AE can arise from any use of the drug (e.g., off-label use, use in combination with another drug) and from any route of administration, formulation, or dose, including an overdose.

A suspected adverse reaction is any AE for which there is a reasonable possibility that the drug caused the AE.

AEs do not include the following:

- Stable or intermittent chronic conditions (such as myopia requiring eyeglasses) that are present prior to Baseline and do not worsen during the study

- Medical or surgical procedures (e.g., surgery, endoscopy, tooth extraction, transfusion). The condition that leads to the procedure is an AE if not present at Baseline.
- Overdose of concomitant medication without any signs or symptoms unless the subject is hospitalized for observation; if an overdose occurs, it will be reported on an overdose form
- Hospitalization for elective surgery planned prior to study (situation where an untoward medical occurrence has not occurred)
- Pregnancy will not be considered an AE, but if it occurs, it will be reported on a pregnancy form

7.1.2 Definition of Serious Adverse Event

In addition to the severity rating, each AE will be classified by the Investigator as “serious” or “not serious.” The seriousness of an event will be defined according to the applicable regulations and generally refers to the outcome of an event. An SAE is one that meets one or more of the following:

- Is fatal
- Is immediately life threatening
- Results in disability or permanent damage
- Requires hospitalization
- Prolongs existing hospitalization
- Is a congenital anomaly or birth defect (in an offspring)
- Is medically significant

Definition of Life Threatening

A life-threatening event places the subject at immediate risk of death from the event as it occurred. This does not include an AE, which, had it occurred in a more severe form, might have caused death.

Definition of Hospitalization

Hospitalization is defined by the Sponsor as a full admission to the hospital for diagnosis and treatment. This includes prolongation of an existing inpatient hospitalization.

Examples of visits to a hospital facility that do **not** meet the serious criteria for hospitalization include:

- Emergency room visits (that do not result in a full hospital admission)
- Outpatient surgery
- Preplanned or elective procedures
- Protocol procedures
- Social hospitalization, defined as admission to the hospital as a result of inadequate family support or care at the subject's primary residence

Definition of Disability or Permanent Damage

Disability is defined as a persistent or significant incapacity or substantial disruption of the ability to conduct normal life functions.

Definition of Medically Significant

Important medical events (medically significant events) that may not result in death, be life threatening, or require hospitalization may be considered to be an SAE when, based upon appropriate medical judgment, they may jeopardize the subject or may require medical or surgical intervention to prevent one of the outcomes listed in this definition. Examples of such events are intensive treatment in an emergency room or at home for allergic bronchospasm, blood dyscrasias, or convulsions that do not result in hospitalization or development of drug dependency or drug abuse.

An SAE may also include any other event that the Investigator or Medical Monitor judges to be serious or that suggests a significant hazard, contraindication, side effect, or precaution.

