Seizures are common, although not diagnostic. Commonly observed symptoms include awake breathing disruptions, scoliosis, and interest in social interaction (intense eye communication) (Neul et al. 2010; Percy et al. 2010). Gastrointestinal symptoms, including constipation and chewing and swallowing difficulties, are observed in the majority of patients with RTT (Motil et al. 2012). Sudden changes in mood, screaming and inconsolable crying are common behaviors in children and adolescents with RTT (Mount et al. 2001, 2002; Robertson et al. 2006; Cianfaglione et al. 2015). These impairments can further exacerbate

other symptoms and disrupt activities of daily living including educational, recreational and treatment opportunities (Epstein et al. 2016; Perry et al. 1991; Thompson and Iwata 2001; Iemmi et al. 2016). Autonomic manifestations, which include abnormalities in cardiac and respiratory function, as well as in peripheral circulation, are considered to be predominantly of central nervous system origin. Rett syndrome is also characterized by impaired growth affecting the brain and other organ systems.

Loss of purposeful hand use is a defining aspect of RTT during the onset of regression and at least 30% of individuals remain without any type of purposeful hand use (Downs et al. 2010). Individuals with some purposeful hand movements vary in their level of ability to reach for and grasp objects. The ability to self-feed is observed in 25-43% (Cass et al. 2003; Larsson et al. 2005; Downs et al. 2011). Poorer levels of hand function are associated with both age and severity of mobility impairment (Downs et al. 2011).

In adulthood, a late motor deterioration stage occurs, characterized by worsening dystonia, rigidity, and in some cases deterioration in the ability to walk and parkinsonian symptoms. Affected individuals have a yearly death rate between 1% and 2%, with 25% of all deaths characterized as sudden and unexpected (Kerr et al. 1997; Samaco and Neul 2011). Women with RTT can survive into their fifties and occasionally longer (Samaco and Neul 2011).

There are no medicines approved for the treatment of RTT. Treatment focuses on the management of each patient's symptoms and, even in that regard, is often unsatisfactory and has only a limited effect on functional improvement. Accordingly, the burden on families and other caregivers is very great (Palacios-Ceña et al. 2018).

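### The elective-procedure exclusion in Protocol 7.1.2 is wider than the exemption in 7.1.1, so an elective admission for a condition that arose or worsened on study need not meet the hospitalization criterion for an SAE

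*Protocol*

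**What the plan says.** **Seriousness (Protocol 7.1.2).** An AE that requires hospitalization is serious. "Hospitalization is defined by the Sponsor as a full admission to the hospital for diagnosis and treatment". A list then gives examples of hospital visits that do not "meet the serious criteria for hospitalization include"; one entry is "Preplanned or elective procedures". The neighbouring entries carry their own limits: emergency room visits are excluded only if no full admission follows, and social hospitalization is defined. The elective entry has no limit of timing or cause.

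**What is an AE (Protocol 7.1.1).** Three of the listed exclusions bear on the same situation:
- chronic conditions "that are present prior to Baseline and do not worsen during the study";
- procedures themselves, with the rider "The condition that leads to the procedure is an AE if not present at Baseline";
- "Hospitalization for elective surgery planned prior to study (situation where an untoward medical occurrence has not occurred".

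**Dating and counting.** Protocol 7.2.3 allows an AE to start on the date of a significant, sustained worsening. Protocol 9.5.2 and SAP 14.2 define a TEAE by a start after the first dose and within 30 days of the last dose. TEAEs and SAEs are both primary endpoints (Protocol 2.1.1, SAP 14.1).

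**The concern.** Section 7.1.1 ties its hospitalization exemption to planning before the study and to the absence of an untoward event. Section 7.1.2 carries neither limit. If a condition appears or worsens on trofinetide and the resulting full admission is booked in advance, the most concrete seriousness criterion can be set aside because the admission was elective. Whether the event is an SAE then depends on less definite routes, and two sites could classify the same event differently.

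The rider on procedures adds uncertainty one step earlier. It makes the underlying condition an AE if it is new, and does not say what happens if it was present at Baseline and got worse.

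The study is exposed to this. It is uncontrolled and its main product is a set of descriptive safety rates. Baseline is the end of a 40-week open-label study, so conditions that began on drug in the antecedent studies may already be present at Baseline here. The background section says "Commonly observed symptoms include awake breathing disruptions, scoliosis", and puts gastrointestinal symptoms, including chewing and swallowing difficulties, in the majority of patients. Worsening of such conditions over a long extension is plausible. The SAP plans no separate summary of hospitalizations or procedures in which a misclassified admission would show. SAP 5.8 to 5.10 resolve unclear onset, missing severity and missing relationship conservatively, but no convention covers seriousness.

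**Working it through.** The point turns on wording, so the rules are applied to each kind of elective admission in turn.

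| Elective full admission for | AE under 7.1.1? | Hospitalization criterion in 7.1.2 met? |
|---|---|---|
| A stable Baseline condition, planned before the study | No | No |
| A stable Baseline condition, planned on study | No: a procedure is not itself an AE and the condition has not worsened | No (the question does not arise) |
| A condition new after the first dose | Yes, by the rider on procedures | No, because elective |
| A Baseline condition that worsened after the first dose | Yes by the chronic-condition exclusion read with 7.2.3; the rider is silent | No, because elective |

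The first two rows are consistent. In the last two there is an AE that led to a full admission, yet the hospitalization criterion need not be met.

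**What remains for those two rows.** The 7.1.2 list removes one criterion only. The others that could apply are:
- disability or permanent damage, and immediate threat to life, where the facts meet them;
- medical significance, for events where "they may jeopardize the subject or may require medical or surgical intervention to prevent one of the outcomes listed in this definition";
- any other event that the Investigator or Medical Monitor judges serious.

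The last two are written with *may*, and the note on terms in the protocol synopsis says that *may be* means allowed, not required. A definite criterion is thus replaced by discretion.

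**TEAE count.** Worsening after the first dose can be dated from that worsening (7.2.3). It then starts inside the TEAE window of Protocol 9.5.2 and SAP 14.2 and is counted. It is lost only if a site reads the rider as meaning that a condition already present at Baseline is never an AE once a procedure follows.

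**Scale.**
- Planned number (Protocol 9.3): 180 × 0.85 = 153, which reproduces the stated figure.
- One subject: 100 × 1/153 = 0.65 percentage points of SAE incidence.
- The number of affected subjects is not in the documents. For scale only, assuming 1, 3, 5 or 8 affected subjects with no other SAE gives 0.65, 1.96, 3.27 or 5.23 points.

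**The case against.** The strongest reply is that the two sections answer different questions. Section 7.1.1 decides what is an AE and 7.1.2 decides when an AE is serious. An admission can fall outside the first exemption and still fail the hospitalization criterion without contradiction; it is then an AE whose seriousness rests on the other criteria. Section 7.1.2 also says that seriousness follows the applicable regulations, and worsening that needs surgery fits the medically significant clause well. This stands as far as it goes: there is no strict contradiction, and many such events may be reported correctly. It does not remove the gap, because the routes most likely to apply are discretionary.

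Three stronger readings are tempting and are not supported:
- *Every elective admission is non-serious.* Section 7.1.2 removes only the hospitalization criterion; the rest remain open.
- *Section 7.1.1 contradicts itself on worsened conditions.* The rider says if, not only if. It is silent on worsening, while the chronic-condition exclusion and 7.2.3 point towards recording it.
- *Most subjects enter with conditions that lead to planned surgery.* The background section reports symptoms as common; it says nothing about surgery or admission.

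**Conclusion.** The concern holds for the SAE count. As written, a full elective admission arranged on study for a condition that arose or worsened after the first dose need not meet the hospitalization criterion. It then reaches the SAE tables only through another criterion or by judgment. The likely direction of error is understatement, and sites can differ.

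For the TEAE count the support is weak. A reader might infer that these events drop out of it as well, but that needs the narrow reading of the rider.

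The size is unknown. The 0.65 points per subject assumes 153 subjects treated and that the affected subject has no other SAE; if she has one, subject-level incidence does not change. A reader might apply an assumed yearly admission rate to the planned follow-up and quote an undercount. The documents support no such rate, and the result would be an upper limit under that rate, since some events would still be reported by other routes.

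The point deserves correction and is more than a missing detail, because following the definition as written can lower a primary endpoint.

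**What to change.** Reconcile the passages with two changes to the reporting definitions:

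1. In 7.1.2, limit the entry to preplanned or elective procedures for a condition that did not arise or worsen after the first dose in this study. Elective procedures for stable conditions stay excluded, whenever they were scheduled.
2. In 7.1.1, extend the rider on procedures so that the condition is an AE if it was not present at Baseline *or has worsened since Baseline*.

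For data already collected, query sites on AEs that led to an elective admission, so that the Investigator can reassess seriousness before database lock. Seriousness is the Investigator's classification, so data management should not recode it alone. A query that starts from recorded AEs will not find a worsening that was never recorded; this matters only where a site took the narrow reading of the rider.

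The cost is two lines of protocol text, one round of queries, a few more SAE forms and a slightly higher reported SAE rate. No dose, visit or treatment changes.

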7.2 Classification of an Adverse Event

7.2.1 Severity of Event

The severity of each AE will be graded on a 3-point scale and reported in detail as indicated on the eCRF:

- **Mild:** awareness of sign or symptom but easily tolerated, causing minimal discomfort, and not interfering with normal everyday activities
- **Moderate:** sufficiently discomforting to interfere with normal everyday activities
- **Severe:** incapacitating and/or preventing normal everyday activities

7.2.2 Relationship to Study Drug

The causality of each AE should be assessed and classified by the Investigator as “related” or “not related.” An event is considered related if there is a reasonable possibility that the event

may have been caused by the product under investigation (i.e., there are facts, evidence, or arguments to suggest possible causation).

Consider the following when assessing causality:

- Temporal associations between the agent and the event
- Response to cessation (de-challenge) or re-challenge
- Compatibility with known class effect
- Known effects of concomitant medications
- Pre-existing risk factors
- A plausible mechanism
- Concurrent illnesses

7.2.3 Duration

The start and stop dates for AEs will be recorded using the following criteria:

- **Start:** Date of the first episode of the AE or date of significant sustained worsening in severity
- **Stop:** Date when AE either ceased permanently or changed in severity

For AEs of diarrhea, the start date and stop date of a decrease in severity will also be recorded.

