7.3 Time Period and Frequency for Event Assessment and Follow-Up

Adverse events with an onset before the first dose of open-label trofinetide in the present study will be recorded as an AE in the antecedent study. All ongoing AEs from the antecedent trofinetide study will be carried over after informed consent has been obtained for the present study and recorded from Baseline for the present study until resolution or the follow-up safety assessment. An adverse event occurring after the first dose of open-label trofinetide in the present study will be recorded as an AE in the present study. Adverse events for the present study will be recorded from the time of first dose of open-label trofinetide in the present study through the safety follow-up period.

All AEs must be either resolved or stable at the end of the safety follow-up period. If an AE is ongoing at the end of the study safety follow-up period, every reasonable attempt should be made to follow and appropriately treat the subject until the AE resolves or until the Investigator deems the AE to be chronic or stable.

In the event that a subject discontinues and has an ongoing AE at the time of discontinuation ([Section 4.4.2](#)) or is withdrawn from the study because of an AE, the subject should be followed and appropriately treated until the AE resolves or until the Investigator deems the AE to be chronic or stable.

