### **5.8       Missing or incomplete Date for Adverse Events**

Missing or incomplete adverse event (AE) start dates will be imputed for the purpose of determining whether the AEs are treatment-emergent or not (see [Section 14.2](#) for definition). When the chronological order of an AE onset relative to the study drug treatment period is unclear due to missing or incomplete date(s), the AE will be considered as treatment-emergent. The imputation algorithms will be detailed in the analysis dataset specification document. The missing or incomplete dates captured on the eCRF will be displayed in the data listings.

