### **14.2 Adverse Events**

Adverse events will be coded using MedDRA dictionary, Version 23.0 or newer.

An AE (classified by preferred term) will be considered a treatment-emergent AE (TEAE) if started after first dose administration and no later than last dose date + 30 days.

The event counts, the number, and percentage of subjects reporting TEAEs in the treatment group of the antecedent DB study and overall will be tabulated by system organ class (SOC) and preferred term; by SOC, preferred term, and maximum severity; and by SOC, preferred term, and relationship to study drug. If more than one TEAE occurs with the same preferred term for the same subject, then the subject will be counted only once for that preferred term using the most severe and most related occurrence for the summarization by severity and by relationship to study drug. The display in these tables will be sorted alphabetically by SOC and then by descending subject frequency for the preferred terms (combined counts from overall group) within each SOC.

The event counts, the number and percentage of subjects with any TEAEs will also be tabulated by preferred term without SOCs. This table will be sorted by descending subject frequency.

The incidence of most frequently reported (preferred terms reported by  $\geq 5\%$  of subjects overall) TEAEs, SAEs reported after treatment start, TEAEs leading to drug withdrawn, and TEAEs related to study drug will be summarized by SOC and preferred term. The tables will be sorted alphabetically by SOC and then by descending frequency within each SOC in overall group. In

addition, the incidence of fatal treatment-emergent AEs (i.e., events that cause death) will be summarized separately by SOC and preferred term.

These summary tables except for the most frequently reported TEAEs tables will also be presented by relationship to COVID-19 related Infection (Not related to COVID-19 Infection vs. Related to COVID-19 Infection).

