An AE listing by subject will display all events, including those which are not treatment-emergent, and will include the verbatim term in addition to the MedDRA SOC and preferred term. This listing will also include all relevant eCRF data associated with the event: date of onset, date resolved, date of last dose, severity, frequency, outcome, relationship to study drug, and action taken with study drug. Separate listings will be presented for treatment-emergent SAEs, related TEAEs, TEAEs leading to drug withdrawn, fatal TEAEs (if any), and TEAEs Related to COVID-19 Infection.

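### Diarrhoea severity is dated, but the SAP's AE tables have no time axis: they cannot show whether diarrhoea persists, and they omit diarrhoea carried over unchanged and withdrawals caused by it

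*Protocol*

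**What the plan says.** Protocol 7.2.3 starts an AE at its first episode or at a significant sustained worsening. The stop is the "Date when AE either ceased permanently or changed in severity". For diarrhoea alone it adds: "For AEs of diarrhea, the start date and stop date of a decrease in severity will also be recorded".

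Protocol 7.3 assigns an AE with onset before the first dose here to the antecedent study, and then says: "All ongoing AEs from the antecedent trofinetide study will be carried over after informed consent has been obtained for the present study". Such events are followed until resolution or the safety follow-up.

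Under SAP 14.2 an AE is treatment-emergent if it "started after first dose administration and no later than last dose date + 30 days". The tables give event counts and the number and percentage of subjects by system organ class and preferred term, by maximum severity and by relationship. When a preferred term repeats within a subject, "then the subject will be counted only once for that preferred term using the most severe and most related occurrence". Further tables cover frequent TEAEs, fatal TEAEs, a COVID-19 split, and "SAEs reported after treatment start, TEAEs leading to drug withdrawn, and TEAEs related to study drug". The by-subject listing holds all events, treatment-emergent or not, with "date of onset, date resolved, date of last dose, severity, frequency, outcome, relationship to study drug, and action taken with study drug".

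Three other places bear on this. Under SAP 5.8, when the order of onset and dosing is unclear, "the AE will be considered as treatment-emergent". SAP 6 tabulates reasons for discontinuation but specifies no preferred term. Protocol 2.1.1 and SAP 14.1 both list withdrawals due to AEs, not only TEAEs, as a primary endpoint.

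**The concern.** The primary objective is the safety and tolerability of continued long-term treatment, in subjects who have already completed 40 weeks of the antecedent study and may be treated for up to about 32 months more. Diarrhoea was the most common AE across all groups in both Phase 2 Rett studies (Protocol 1.3), and the synopsis names it as the example reason for reducing or holding doses. For a common, usually non-serious event, the long-term question is whether it settles or persists. The sponsor collects the dates needed to answer this, but no planned table uses them.

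Diarrhoea that began in the antecedent study and never changed is the clearest case of a persistent tolerability problem. It is also the case that the TEAE tables leave out. If it ends in withdrawal, the table for that primary endpoint does not name it.

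**Working it through.** **Planned N.** Protocol 9.3: 180 × 0.85 = 153. This reproduces the stated figure. The study is descriptive, so there is no power calculation to check.

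**Applying the recording and counting rules to constructed histories** (Protocol 7.2.3 and 7.3; SAP 14.2; days are study days):

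| History | Days with diarrhoea on study | Events | TEAE subjects | Worst grade |
|---|---|---|---|---|
| New, moderate, Day 10 to 13 | 3 | 1 | 1 | moderate |
| New, moderate, Day 10 to 910 | 900 | 1 | 1 | moderate |
| Carried over, moderate, unchanged to Day 910 | 909 | 0 | 0 | none |

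The first two rows are identical in every tabulated field, provided they also match on relationship, seriousness and withdrawal. The third has the longest exposure to diarrhoea and no entry.

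**Logical bounds on what the tables leave open.** Take one mild, related, non-serious TEAE per affected subject, onset on Days 2 to 83, and no dropout. The Phase 2 dose-group rates in Protocol 1.3 give 0.13 × 153 = 19.9 (20), 0.27 × 153 = 41.3 (41) and 0.56 × 153 = 85.7 (86) affected subjects. The AE tables are the same whether none or all of the 20, 41 or 86 still have diarrhoea in Weeks 52 to <104 (Days 364 to 727). These are bounds, not expected effects.

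**Unchanged carry-over.** The documents give no rate, so I assume 5%, 10% or 20%: 0.05 × 153 = 7.65 (8), 0.10 × 153 = 15.3 (15), 0.20 × 153 = 30.6 (31). If the onset is known and severity does not change, these subjects add 0 to the TEAE diarrhoea row. Worsening would make the event a TEAE, unclear onset defaults to TEAE, and a serious event may enter the table of SAEs after treatment start.

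**Withdrawal.** A subject who stops because of unchanged carried-over diarrhoea adds 0 to the table of TEAEs leading to drug withdrawal, and 1 to the discontinuation reasons in disposition, without a preferred term. The cause can be found only in the listing.

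**Conditional on storage.** The documents do not say whether a dated decrease becomes a new AE record. If it does, and nothing joins the phases:
- A severe-moderate-mild episode resolving in 30 days gives 3 events; a severe episode lasting 900 days gives 1. Both give 1 subject, worst grade severe.
- Of 41 single episodes, none stepping down gives 41 events, a quarter stepping down once gives 41 + 10 = 51, and all stepping down once gives 82. Joined phases give 41 throughout.
- If all carried-over cases improve one grade, the assumed 8, 15 or 31 subjects become TEAE subjects: 8/153 = 5.2%, 15/153 = 9.8%, 31/153 = 20.3%.

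If a decrease is only an extra field on the same record, none of these three effects occurs.

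**Why a by-period table needs the number at risk.** Suppose 41 subjects have persistent diarrhoea and 20 of them leave. Prevalence falls from 41/153 = 26.8% to 21/133 = 15.8% with no episode resolved.

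**Precision available.** With k affected subjects, the 95% half-width for a persistent share p is 1.96 × √(p(1−p)/k). For p = 20% it is 17.5 points at k = 20 and 8.5 at k = 86; for p = 50% it is 21.9 and 10.6.

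**The case against.** **Nothing promised is missing.** Protocol 9.5.2 asks for TEAEs by class and term, maximum severity and relationship, and for TEAEs leading to discontinuation. It plans no duration analysis, and the SAP matches it. This stands: the point is a missed opportunity, not a conflict between the documents.

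**Leaving out pre-dose events is ordinary for a treatment-emergent definition, and the data are kept.** Also true: the listing shows every event, with dates, outcome and action taken. A duration table could be added at reporting without an error-rate cost. But a listing does not summarise a primary endpoint, and that endpoint is worded as withdrawals due to AEs.

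**A reader might infer that the counts move the wrong way as written, so that improvement inflates them.** The documents do not support this. Protocol 7.2.3 defines a start as a first episode or a sustained worsening, so a decrease is not a start. The diarrhoea sentence says the dates are recorded, not that a new AE is created. The stop rule leans towards separate records, but the eCRF layout decides and it is not shown. Even with split records, diarrhoea starting on study changes only the event count, since each subject counts once per term at worst grade. Worsening splits records too, so the effect would not be confined to improvement. What remains is a request for a stated counting rule.

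**The illustrative rates may not transfer.** They come from subjects aged 5 to 15 in a short study. Assigned doses here are mostly at or above the top Phase 2 dose of 200 mg/kg: 6 g at 20 kg is 300 mg/kg, 10 g at 50 kg is 200 mg/kg. Reductions to 3 g are allowed, and everyone has already completed 40 weeks of the antecedent study. The rates serve only to scale the bounds.

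**Conclusion.** The point holds as a low-cost improvement that the sponsor should make. The planned AE tables cannot show whether diarrhoea resolves or persists. They leave diarrhoea carried over unchanged out of every TEAE table, and they miss a withdrawal caused by it. These conclusions follow from the text and do not depend on how the eCRF stores severity phases.

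The size cannot be estimated from the documents. The 8 to 31 subjects absent from the TEAE row rest on an assumed carry-over share of 5% to 20%, a known earlier onset and unchanged severity. The range of 0 to 20, 41 or 86 subjects with diarrhoea in the second year is a logical bound.

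The stronger inference, that improving diarrhoea is counted more often than diarrhoea that never improves, is not established. The 51 and 82 events and the 5.2% to 20.3% of subjects apply only if each dated decrease is stored and counted as a new record.

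**What to change.** Add to SAP 14.2:

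1. **Diarrhoea by period.** For each exposure period in SAP 10.1, give the number and percentage of subjects with diarrhoea by worst grade in that period, including carried-over ongoing events. Beside it, show the number at risk and the number who left with ongoing diarrhoea.
2. **Withdrawals.** Tabulate all AEs leading to drug withdrawal by preferred term, whether or not treatment-emergent.
3. **Optional: duration.** Summarise episode duration or Kaplan-Meier time to resolution, censoring ongoing episodes at last contact. Keep Single and Recurrent records (Protocol 7.2.4) separate. Label Recurrent results as upper bounds, here and in item 1, because such a record can span diarrhoea-free days.
4. **Counting rule.** If the eCRF stores each dated severity phase as its own record, count contiguous phases as one episode and do not flag a decrease in a carried-over event as a new TEAE. A worsening stays a TEAE.

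The cost is one SAP paragraph and two or three tables, with no new data collection. Limits to state with the results: dates are caregiver-reported; scheduled visits are up to 52 weeks apart (Week 52 to Week 104); Protocol 6.3 does not name diarrhoea as diary content; completers who start commercial drug within 30 days have no follow-up contact; and later periods will hold fewer subjects. The diarrhoea result may also look less favourable than a single incidence figure.
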